APPENDIX II TOXICITY GRADING SCALE

EVENT	MILD (Grade 1)	MODERATE (Grade 2)	SEVERE (Grade 3)	POTENTIALLY LIFE THREATENING (Grade 4)
Fever	≥100.4-101.1°F (≥38.0-38.4°C)	≥101.2-102°F (≥38.5-39°C)	≥102.1°F-104°F (≥39°C-40°C)	>104°F
Headache	No interference with activity	Some interference with activity, may require repeated use of non-narcotic pain reliever for more than 24 hours	Significant, prevents daily activity, any use of narcotic pain reliever	ER visit or hospitalization
Fatigue	No interference with activity	Some interference with activity	Significant, prevents daily activity	ER visit or hospitalization
Myalgia	No interference with activity	Some interference with activity	Significant, prevents daily activity	ER visit or hospitalization
Nausea	No interference with activity	Some interference with activity	Significant, prevents daily activity	ER visit or hospitalization for hypotensive shock
Vomiting	1-2 episodes/24 hours	>2 episodes/24 hours	Requires IV hydration	ER visit or hospitalization for hypotensive shock
Diarrhea	2-3 loose stools or <400 g/24 hours	4-5 stools or 400-800 g/24 hours	6 or more watery stools or >800 g/24 hours or requires outpatient IV hydration	ER visit or hospitalization
Injection site pain	Does not interfere with activity	Repeated use of non-narcotic pain reliever > 24 hours or interferes with activity	Use of any narcotic pain reliever or prevents daily activity	ER visit or hospitalization
Injection site erythema/redness	25-50 mm	51 mm-100 mm	>100 mm	Necrosis or exfoliative dermatitis
Injection site induration/swelling	25-50 mm and does not interfere with activity	51 mm-100 mm or interferes with activity	>100 mm or prevents daily activity	Necrosis

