Details of visits, visit windows, and procedures are provided in the Schedule of Events below. After signing the informed consent form, subjects will undergo screening procedures up to 30 days before a single-dose injection on Day 1. Subjects will be observed in clinic for 30 minutes after injection and vital signs obtained at least 30 minutes but no more than 60 minutes after injection. Local and systemic solicited adverse events (AEs) occurring within 7 days after injection (to Day 8) will be recorded by the subject using a memory aid. Subjects will be specifically asked to record local injection site events (pain, redness, swelling) and systemic events (oral temperature \geq 100.4° F, chills, fatigue, headache, myalgia, joint pain, and nausea). Memory aids will be reviewed at the Day 8 visit. Unsolicited AEs will be monitored from Day 1 through Day 29; serious adverse events (SAEs) and adverse events of special interest (AESI) will be monitored for the duration of the study (to Day 183). Information on all concomitant medications used through Day 29 will be recorded; after Day 29, only information on concomitant medications used for the treatment of an SAE or AESI will be recorded. After screening, blood will be collected for immunogenicity assessments at Days 1 (pre-vaccination), 8, 15, 22, and 57.

Subjects who discontinue study participation before Day 22 (or who do not undergo Day 22 plasmapheresis for other reasons) may be replaced.

A final analysis of data collected throughout the study from all subjects will be performed after the last subject has completed the study and the immunogenicity and safety data have been cleaned and locked.

Serology: Serum neutralizing antibody (SNA) responses to CHIKV VLP will be determined by a luciferase based anti-CHIKV neutralization assay (CHIKV-luc). Titers are expressed as the reciprocal of the serum dilution achieving 80% neutralization (NT₈₀). Anti-CHIKV specific IgG and IgM antibody levels will be determined by enzyme-linked

immunosorbent assay (ELISA). Peripheral blood mononuclear cells will be collected for exploratory analyses of T and B cell immune responses.

Number of Subjects (Planned): 25

Study Population: Healthy adults 18 to 45 years of age

Inclusion Criteria:

Subjects must meet **all** the following criteria to be enrolled:

1. Able and willing to provide informed consent voluntarily signed by subject.
2. Any gender, 18 to 45 years of age (inclusive).

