3.3.10 Solicited Adverse Events

Solicited AEs will be collected from IP administration until Day 8. Solicited AEs for this study are local events of pain, redness, and swelling at the injection site and systemic events of oral temperature $\geq 38^{\circ}\text{C}$ (≥ 100.4 degrees Fahrenheit [$^{\circ}\text{F}$]), chills, fatigue, headache, myalgia, arthralgia, and nausea (see Section 7.1.2 and Section 7.1.2.1).

Subjects will be trained to complete a memory aid to observe, measure, and record these solicited AEs. To measure oral temperature, a digital thermometer will be provided to the subject to measure their temperature each day and record them in their memory aid. To record injection site local reactions, a ruler will be provided to the subject to measure and record the diameter of redness and swelling at the largest point of the reaction each day.

Study staff will review the signs and symptoms recorded in the memory aid. The Investigator will then assess all solicited AEs for severity (Section 7.1.7) and the action taken, and causality (Section 7.1.8). The results of the Investigator's assessment will be recorded as a separate source document and will be entered on the solicited AE CRF. Symptoms continuing beyond the solicited AE collection period will be collected and recorded on the AE CRF.

Details on definition, evaluation, reporting periods and documentation are outlined in Section 7.

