APPENDIX II GRADING SCALE

EVENT	MILD (Grade 1)	MODERATE (Grade 2)	SEVERE (Grade 3)	POTENTIALLY LIFE THREATENING (Grade 4)
Fever	$\geq 100.4-101.1^{\circ}\text{F}$ ($\geq 38.0-38.4^{\circ}\text{C}$)	$\geq 101.2-102^{\circ}\text{F}$ ($\geq 38.5-39^{\circ}\text{C}$)	$\geq 102.1^{\circ}\text{F}-104^{\circ}\text{F}$ ($\geq 39^{\circ}\text{C}-40^{\circ}\text{C}$)	$>104^{\circ}\text{F}$ ($>40^{\circ}\text{C}$)
Headache	No interference with activity	Some interference with activity, may require repeated use of non-narcotic pain reliever for more than 24 hours	Significant, prevents daily activity, any use of narcotic pain reliever	ER visit or hospitalization
Fatigue	No interference with activity	Some interference with activity	Significant, prevents daily activity	ER visit or hospitalization
Myalgia	No interference with activity	Some interference with activity	Significant, prevents daily activity	ER visit or hospitalization
Nausea	No interference with activity	Some interference with activity	Significant, prevents daily activity	ER visit or hospitalization
Chills	No interference with activity	Some interference with activity not requiring medical intervention	Prevents daily activity and requires medical intervention	ER visit or hospitalization
Arthralgia	No interference with activity	Some interference with activity not requiring medical intervention	Prevents daily activity and requires medical intervention	ER visit or hospitalization
Injection site pain	Does not interfere with activity	Repeated use of non-narcotic pain reliever > 24 hours or interferes with activity	Use of any narcotic pain reliever or prevents daily activity	ER visit or hospitalization
Injection site erythema/redness	25-50 mm*	>50 mm-100 mm*	>100 mm*	Necrosis or exfoliative dermatitis
Injection site induration/swelling	25-50 mm* and does not interfere with activity	>50 mm-100 mm* or interferes with activity	>100 mm* or prevents daily activity	Necrosis

*Revised by Sponsor

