5.8 Adverse Event Toxicity/Severity Grading

With the exception of redness and swelling, all solicited AEs are graded by the Investigator according to severity grading scales from "mild" to "potentially life-threatening." The

severity of redness and swelling, recorded as a diameter (mm) in the solicited adverse event memory aid, is summarized according to categories based on the largest-diameter linear measurement when a local reaction is present:

- Grade 0/absent = 0-24 mm.
- Grade 1/mild= 25-50 mm.
- Grade 2/moderate= 51-100 mm.
- Grade 3/severe= >100 mm.
- Grade 4/potentially life threatening = necrosis or exfoliative dermatitis.

Events reported as not present (0 mm is entered) are reported as Grade 0. Similarly, body temperatures recorded by the subject that are below 100.4° result in fever reported as Grade 0/absent.

Unsolicited AEs and solicited AEs other than redness and swelling are graded by the Investigator for severity. The severity grading scales (Grade 1 = Mild, Grade 2 = Moderate, Grade 3 = Severe, Grade 4 = Potentially Life-Threatening) that are used for safety assessment in this study are provided in Appendix II of this document and Section 7.1.7 and Appendix II of the Protocol, based on the *FDA Guidance for Industry: Toxicity Grading Scale for Healthy Adult and Adolescent Volunteers Enrolled in Preventative Vaccine Clinical Trials* (1). Note that AEs that result in death are classified as Grade 4 and indicated as resulting in death.

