6.2 Units and Precision

No intermediate rounding will be performed in SDTM datasets; only final values for TLFs will be rounded as follows. Immunogenicity titers will be reported with one decimal place or two significant digits (e.g., 0.032, 18.0).

Vital signs data will be reported using standard international units. Vital signs variables including derivations thereof will be reported to the same precision as the source data. Parameters derived directly from source data (e.g., minimum, maximum) or first-order statistics (e.g., mean) will be reported and analyzed with the same precision as the source data. Second-order statistics (e.g., SD) will be reported with one more significant digit than the source data. Percentages will be reported to one decimal place.

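### The fever row of both grading scales puts 39.0°C in Grade 2 and in Grade 3, and its °C bands do not match its °F bands at two grade boundaries

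*SAP*

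**What the plan says.** The fever row in SAP Appendix II gives each of Grades 1 to 3 as a °F band with a °C band in parentheses:

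- Grade 1: "≥100.4-101.1°F (≥38.0-38.4°C")
- Grade 2: "≥101.2-102°F (≥38.5-39°C")
- Grade 3: "≥102.1°F-104°F (≥39°C-40°C")

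Grade 4 is anything above 104°F. Protocol Appendix II has the same bands and adds the °C equivalent (above 40°C) to Grade 4. Neither document says how to grade a reading that meets two bands, or which unit governs.

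On the unit of the memory aid, the protocol synopsis and SAP 2.2 give the fever threshold in °F only. Protocol 3.3.10 and 7.1.2.1 give it in both units. Protocol 3.3.10 also says that "a digital thermometer will be provided to the subject to measure their temperature each day and record them in their memory aid", without naming a unit. SAP 5.8 adds that "body temperatures recorded by the subject that are below 100.4° result in fever reported as Grade 0/absent", with no unit letter.

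Under Protocol 3.3.10 and SAP 5.8 the Investigator grades fever using the severity scale. SAP 9.2.2 then tabulates solicited events by maximum severity and, separately, those of Grade 3 or higher (Tables 14.3.2.2 and 14.3.2.3). SAP 9.2.1 also has a line for solicited events of Grade 3 or higher.

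**The concern.** Fever is the one systemic solicited event with purely numeric grades, so the scale should give each reading one grade. At 39.0°C it gives two, and at two other readings the grade depends on the unit. Two Investigators, or one Investigator on two days, could grade the same temperature differently and both be following the scale. The boundary that matters most is between Grades 2 and 3, because it decides whether a subject is counted as having severe fever.

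**Working it through.** **Inputs.** The °F and °C bands are those of SAP Appendix II, and Grades 2 and 3 are the same in Protocol Appendix II. The planned sample is 25 subjects (Protocol 3.1.2, SAP 2.2). The plan states no figure to reproduce here.

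**Step 1: overlap within the °C bands.** Grade 2 runs from 38.5 up to and including 39. Grade 3 starts at 39, included. So 39.0°C is in both. In °F, 39.0 × 9/5 + 32 = 102.2, which lies in 102.1 to 104 and is Grade 3 only.

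**Step 2: convert each °F edge,** with C = (F − 32) × 5/9, and read the grade from each set of bands.

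| °F reading | °C | Grade on °F bands | Grade on °C bands |
|---|---|---|---|
| 100.4 | 38.00 | 1 | 1 |
| 101.1 | 38.39 | 1 | 1 |
| 101.2 | 38.44 | 2 | none (between 38.4 and 38.5) |
| 102.0 | 38.89 | 2 | 2 |
| 102.1 | 38.94 | 3 | 2 |
| 102.2 | 39.00 | 3 | 2 and 3 |
| 104.0 | 40.00 | 3 | 3 |

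**Step 3: scan all readings.** Every 0.1°F reading from 100.0 to 104.5 and every 0.1°C reading from 37.8 to 40.3 was graded on both sets of bands.

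- The °F bands used alone give exactly one grade to every 0.1°F reading.
- The °C bands used alone give two grades at a single 0.1°C reading, 39.0°C.
- Across units, the only 0.1°F readings that disagree are 101.2, 102.1 and 102.2.

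**Step 4: which readings reach the Grade 3 or higher table.** They are 102.1°F and 102.2°F if graded on the °C bands, and 39.0°C if recorded in °C. The 101.2°F mismatch is at the boundary between Grades 1 and 2 and cannot affect that table.

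**Step 5: weight of one subject.** 1/25 = 4.0 percentage points.

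**The case against.** The strongest reply is that the memory aid will be in °F, so the overlap will never be met. The synopsis and SAP 2.2 use °F, this is a single US centre, and the value 100.4 in SAP 5.8 can only be °F. Where the protocol gives both units for the threshold they agree exactly, since 100.4°F is 38.0°C. Most of this stands. It places the defect in the °C equivalents and makes it unlikely to matter. It does not remove it, because no section says that °F governs and both operative tables print the overlap.

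A second reply is that the Investigator grades fever. That is so, but the Investigator uses this same row, so judgement does not break the tie.

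A reader might infer three stronger points that the documents do not support:

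- **That SAP 6.2 forces conversion to °C.** It says "Vital signs data will be reported using standard international units". That concerns vital signs, which are taken at screening and on Day 1 and are only listed (Protocol 8.7.5, SAP 9.5.1). Memory-aid temperatures are solicited events, and no section calls for converting them before grading. The °C limits in SAP 6.5.4 (33 and 42) are an example of implausible values, far from any grade boundary.
- **That 101.2°F becomes Grade 1 in °C.** This needs 38.44 to be rounded to 38.4 before grading, which no section asks for. Unrounded, it is in no °C band.
- **That severe-fever counts are unreliable in general.** Only a maximum reading within 38.9 to 39.0°C is exposed, and for a °F reading someone must also grade on the °C bands. No hypothesis is tested (SAP 6.4), and there is no safety committee or interim analysis (SAP 10.1, 10.2). No stated decision depends on this count.

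**Conclusion.** The fever row is wrong as printed in both appendices: 39.0°C has two grades, and the °C and °F bands disagree at 102.1°F and 101.2°F. The conclusion rests only on the printed bands and the standard conversion.

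The effect on results is narrow. If readings are recorded to 0.1°F and graded on the °F bands, which the documents suggest but do not state, there is none. Otherwise a subject whose highest reading is 39.0°C, or 102.1 to 102.2°F graded in °C, could move in or out of the Grade 3 or higher table. The figure of 4 percentage points is the weight of one subject among the 25 planned. It is not a forecast, since the documents give no expected frequency of fever at these readings. This is a minor correction, worth making before any fever is graded.

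**What to change.** - Reconcile the fever row in Protocol Appendix II and SAP Appendix II so that the °C bands do not overlap and correspond to the °F bands. The sponsor should settle the boundary, and both documents should carry the same row.
- Add one sentence saying that the Investigator grades fever on the bands for the unit recorded in the memory aid, without prior conversion, and naming that unit (°F, if the sponsor confirms it).

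Grading stays with the Investigator, as the plan has it, so no programmed derivation of the grade is needed. The cost is one table row per document and one sentence. Procedures and data collection do not change.

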APPENDIX III STANDARD MEDDRA QUERY FOR ARTHRITIS

The following preferred terms include all narrow and broad terms for the Arthritis SMQ for MedDRA version 20.1.

Ankylosing spondylitis
Arthritis
Arthritis allergic
Arthritis bacterial
Arthritis climacteric
Arthritis enteropathic
Arthritis fungal
Arthritis gonococcal
Arthritis helminthic
Arthritis infective
Arthritis reactive
Arthritis rubella
Arthritis salmonella
Arthritis viral
Autoimmune arthritis
Axial spondyloarthritis
Caplan's syndrome
Carcinomatous polyarthritis
Chondrocalcinosis
Chondrocalcinosis pyrophosphate
Chondromalacia
Diffuse idiopathic skeletal hyperostosis
Enteropathic spondylitis
Epidemic polyarthritis
Facet joint syndrome
Felty's syndrome
Gout
Gouty arthritis
Gouty tophus
Haemophilic arthropathy
Infusion site joint infection
Infusion site joint inflammation
Injection site joint infection
Injection site joint inflammation
Juvenile idiopathic arthritis
Juvenile psoriatic arthritis
Juvenile spondyloarthritis

Laryngeal rheumatoid arthritis
Medical device site joint infection
Nodal osteoarthritis
Osteoarthritis
Palindromic rheumatism
Paraneoplastic arthritis
Patellofemoral pain syndrome
Periarthritis
Periarthritis calcarea
Plica syndrome
Polyarthritis
Pyogenic sterile arthritis pyoderma gangrenosum and acne syndrome
Rapidly progressive osteoarthritis
Reiter's syndrome
Rheumatic disorder
Rheumatic fever
Rheumatoid arthritis
Sacroiliitis
Septic arthritis haemophilus
Septic arthritis neisserial
Septic arthritis staphylococcal
Septic arthritis streptobacillus
Septic arthritis streptococcal
Seronegative arthritis
SLE arthritis
Spinal osteoarthritis
Spondylitis
Still's disease
Synovitis
Temporomandibular joint syndrome
Traumatic arthritis
Vaccination site joint infection
Amyloid arthropathy
Ankle arthroplasty
Arthralgia
Arthrodesis
Arthropathy
Arthroscopy abnormal
Arthotoxicity
Articular calcification

Aspiration joint abnormal
Crystal arthropathy
Destructive spondyloarthropathy
Hip arthroplasty
Infusion site joint effusion
Infusion site joint erythema
Infusion site joint movement impairment
Infusion site joint pain
Infusion site joint swelling
Infusion site joint warmth
Injection site joint effusion
Injection site joint erythema
Injection site joint movement impairment
Injection site joint pain
Injection site joint swelling
Injection site joint warmth
Intervertebral discitis
Joint abscess
Joint adhesion
Joint arthroplasty
Joint contracture
Joint crepitation
Joint debridement
Joint destruction
Joint effusion
Joint fluid drainage
Joint range of motion decreased
Joint stiffness
Joint swelling
Joint warmth
Knee arthroplasty
Musculoskeletal stiffness
Neck pain
Neuropathic arthropathy
Osteoarthropathy
Periarticular disorder
Psoriatic arthropathy
Rheumatoid nodule removal
Shoulder arthroplasty
Spinal pain

Spondyloarthropathy
Swollen joint count
Swollen joint count decreased
Swollen joint count increased
Synovectomy
Synovial fluid analysis abnormal
Synovial fluid crystal present
Synovial fluid protein present
Synovial fluid red blood cells positive
Synovial fluid white blood cells positive
Synoviorthesis
Tender joint count
Tender joint count decreased
Tender joint count increased
Traumatic arthropathy
